## 6.4 Measures to Protect the Participant

All participants will have laboratory monitoring of CBC, T4, TSH, Cholesterol, INR, Sirolimus level and complete metabolic panel (CMP) at baseline, 28 days, and 56 days. Side effects may receive imatinib dose reduction to 200 mg daily if persistent. Study withdrawal for side effects is permitted. All side effects will be graded and followed. Side effects suggestive of an infection will prompt cessation of subsequent doses of rapamycin and imatinib mesylate/placebo for 1 week until such symptoms are improved. Any worsening of symptoms would prompt evaluation. Decline in FEV1 or FVC of 10% would prompt end of study, study unblinding, and transition to usual clinical care. A study

coordinator will call each participant to check on how they are doing 1 week +/- 3 days and 2 weeks +/- 3 days after the baseline visit and 2 weeks +/- 3 days after the 1 month study visits.

Study related injuries are addressed in the MUSC Statements of the informed consent form. In the event of a study related injury, the participant should go immediately to the emergency room of the Medical University Hospital, or in case of an emergency go to the nearest hospital, and tell the physician on call that they are in a research study. The doctor should call the study doctor to make arrangements for treatment. If the study sponsor does not pay for treatment, the Medical University Hospital and the physicians who render treatment will bill the participant's insurance. If the insurance company denies coverage or insurance is not available, the participant will be responsible for payment of all services rendered.

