## 5.3.2 Exclusion Criteria

- Current or planned pregnancy or lactation
- Unwillingness to discontinue sirolimus
- Change in the dose or use of sirolimus within the past month
- Inability to perform spirometry
- Other serious illness that would impact the outcome of the study
- Current lung transplant
- Current cigarette smoking
- Required use of ketoconazole, itraconazole, clarithromycin, or rifampin during the 2 months of the study.
- Unwillingness to avoid grapefruit juice or St. Johns Wort during the study.
- Planned surgery during the 2 months of the study..

\*Children are excluded because LAM does not affect children

\*\*Definite or Probable LAM is defined by the ERS LAM guidelines modified by addition of VEGF-D criteria as defined by the MILES Trail

Definite LAM:

1) Characteristic or compatible lung HRCT, and lung biopsy fitting the pathological criteria for LAM; or 2) Characteristic lung HRCT and any of the following: angiomyolipoma (kidney); thoracic or abdominal chylous effusion; lymphangioleiomyoma or lymph-node involved by LAM; and definite or probable TSC.

Probable LAM

1) Characteristic HRCT and compatible clinical history; or

2) Compatible HRCT and any of the following: angiomyolipoma (kidney); thoracic or abdominal chylous effusion; or VEGF-D >800 pg/ml at any time in the past.

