## 5.4 Visit Schedule

**The Baseline Visit** will begin with signing the informed consent. A history and physical examination, post-bronchodilator spirometry, 6 minute walk test distance, and blood samples will be obtained. Questionnaires will be completed and the patient will be randomized to imatinib mesylate, at an oral dose of 400 mg once daily, or placebo stratified on whether sirolimus has been used in the last month. A sirolimus level and VEGF-D level will be measured.

A 1 week trough sirolimus level and telephone call will be obtained on all subjects entering the study on sirolimus therapy.

**1 Month Visit-** Post-bronchodilator spirometry, 6 minute walk test distance, and blood samples will be obtained. Questionnaires will be completed. Sirolimus will be discontinued if used at baseline.

**2 Month Visit/ End of study-** Post-bronchodilator spirometry, 6 minute walk test distance, and blood samples will be obtained. Questionnaires will be completed. A sirolimus level will be obtained to assure drug cessation. The participant is returned to LAM therapy of their choice.

[figure not shown]

Figure 1. Study Schedule, Stratification and Randomization

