## 5.5 Study Examinations 5.5.1 Blood and Urine Samples

These are collected at each study visit.

**Safety:** Universal and Occupational Safety and Health (OSHA) and all institutional-specific (such as bloodborne pathogen training) precautions and training requirements should be followed when processing blood and urine. For more detailed safety information see (http://www.osha.gov/SLTC/biologicalagents/index.html).

Urinalysis, pregnancy test, CBC, TSH, T4, Cholesterol, INR and CMP are performed on samples from each visit at the University Laboratories at MUSC and Columbia to look for adverse events and assure patient health and safety during the study. Trough Sirolimus level is performed on a sample from each visit to verify Sirolimus treated vs. naïve at baseline and that sirolimus was stopped in previous sirolimus receivers at the 1 month visit. This may require participants to take sirolimus at a time of the day that corresponds to anticipated study visit time. VEGF-D levels are performed at each visit to test efficacy of imatinib.

All tests except the VEGF-D will be performed in the clinical laboratory of the institution where the patient is seen (MUSC or Columbia University) and will be performed per standard protocol in these trained and certified laboratories. The costs of laboratory analysis are provided for in the study budget.

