## 6.1.3 Imatinib side effects

The most common side effects of imatinib include nausea, diarrhea, headaches, leg cramps, fluid retention, visual disturbances, rash, weight gain, and reduced number of blood cells (any cell line can be affected). Imatinib is an immune suppressant and increases risks of common and uncommon infections.

Severe systolic congestive heart failure is an uncommon but recognized side effect of imatinib and mice treated with large doses of imatinib show toxic damage to myocardiocytes. Hypoxemia has been noted in one individual with LAM.

Since imatinib is mainly metabolised via the liver enzyme CYP3A4, substances such as ketoconazole, itraconazole, clarithromycin, and grapefruit juice can increase the plasma concentration of the drug. Conversely, CYP3A4 inducers like rifampin and St. John's Wort reduce the drug's activity. These medications will be prohibited during the study. A known interaction between imatinib and sirolimus in which sirolimus levels rise will be monitored during the study.

Imatinib also acts as an inhibitor of CYP3A4, 2C9 and 2D6, increasing the plasma concentrations of simvastatin, cyclosporin, pimozide, warfarin, and metoprolol. Imatinib also reduces plasma levels of levothyroxin via an unknown mechanism. INR, Cholesterol, T4, and TSH will be measured during the study for all individuals.

An imatinib dose reduction to 200 mg daily will be permitted should a participant experience persistent side effects.

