## 6.3 Adverse Events

An adverse event (AE) is any untoward medical occurrence in a study subject. This may include symptom(s), illness, clinically significant abnormal laboratory value or change in value, or worsening in a subject during a clinical study. Since one of the specific aims of the study is to establish the safety of imatinib in LAM affected individuals, it is the goal of the investigators to capture every AE.

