## 6.3.1 Procedures for Adverse Events

Event, date of onset, severity, duration, and relationship to sirolimus or imatinb (if it can be determined) will be recorded on the study AE forms. All adverse events will be followed until they are adequately resolved or stabilized, or for 1 month following study completion, whichever comes first.

If an adverse event occurs during a study visit the study coordinator should first insure the participant receives any needed medical attention. If the study coordinator is notified by phone, the coordinator should confirm that the participant has received medical attention. The study coordinator should then notify the site Principal Investigator and complete the Adverse Event Form within seven days of learning of the event. Study coordinators will comply with local regulations and policies when notifying the institutional IRB.

The following general definitions for rating severity should be used for this study:

**Mild:** Awareness of signs or symptoms, but easily tolerated and transient; causing no loss of time from normal activities; symptoms would not require medication or a medical treatment; signs and symptoms are transient.

**Moderate:** Marked symptoms and discomfort severe enough to cause moderate interference with the subject's usual activities. Symptomatic treatment is possible.

**Severe:** Incapacitating with inability to do work or usual activities; signs and symptoms may be of systemic nature or require medical intervention and/or treatment. Hospitalization may be required or prolonged.

The relationship of an AE or SAE to the underlying disease or to the procedure will be attributed using the following definitions:

Not Related: There is no evidence that the event has a relationship to the drug(s).

**Possibly Related**: The event has a timely relationship to the drug(s) used. However, a potential alternative etiology may be responsible for the adverse event.

**Probably Related**: The event has a timely relationship to the drug(s) used and the causative relationship can clearly be established. No potential alternative etiology is apparent.

The number of subjects and observation time in this pilot study is insufficient to develop a composite index or statistical plan for the evaluation of safety endpoints for this study. Therefore, all adverse events, their timing, severity, and attribution will be reported in study reports.

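### The protocol says imatinib raises warfarin concentrations, yet warfarin users are not excluded and the first INR on treatment is at day 28

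*Combined protocol and SAP*

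**What the plan says.** Section 6.1.3 describes interactions in two directions. It first names agents that change imatinib exposure (CYP3A4 inhibitors and inducers) and says of them: "These medications will be prohibited during the study". A separate, later paragraph says that imatinib itself inhibits CYP3A4, 2C9 and 2D6, "increasing the plasma concentrations of simvastatin, cyclosporin, pimozide, warfarin, and metoprolol". The stated response is to measure INR in everyone during the study.

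The drug exclusion in 5.3.2 is "Required use of ketoconazole, itraconazole, clarithromycin, or rifampin during the 2 months of the study". The next item covers grapefruit juice and St. John's Wort. Neither warfarin nor any other anticoagulant is listed.

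On timing, 6.4 specifies "laboratory monitoring of CBC, T4, TSH, Cholesterol, INR, Sirolimus level and complete metabolic panel (CMP) at baseline, 28 days, and 56 days", and 5.5.1 agrees: "Urinalysis, pregnancy test, CBC, TSH, T4, Cholesterol, INR and CMP are performed on samples from each visit". Under 5.4, blood is drawn at the baseline visit, and at that same visit "the patient will be randomized to imatinib mesylate, at an oral dose of 400 mg once daily, or placebo".

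**The concern.** The protocol identifies a hazard for one kind of participant, leaves her eligible, and then takes no measurement that could show the hazard until treatment is half over. No INR limit or instruction for warfarin appears anywhere in the documents.

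The contrast with sirolimus makes the gap plain. Section 6.1.3 also says that sirolimus levels rise with imatinib. For that interaction the protocol adds a trough level at week 1 (5.4), review by an unblinded team, and dose reduction when the level rises by more than 50% (5.6). Warfarin appears in the same section but gets no early test and no action rule, and no reason is given for the difference.

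What is at stake is participant safety. An INR could rise without symptoms for four weeks and nobody in the study would know. Section 6.1.3 also lists reduced blood cells of any line as a common effect of imatinib, and the CBC follows the same schedule, so a falling platelet count would be missed over the same period.

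**Working it through.** The plan gives no figure to reproduce. The check sets the relevant provisions side by side and then does the schedule arithmetic.

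**Can a warfarin user be enrolled?** Yes, on the text available. Warfarin is not among the exclusions in 5.3.2. The prohibition in 6.1.3 refers to the agents named just before it, which alter imatinib levels; the warfarin statement comes afterwards.

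**When is INR measured?** On days 0, 28 and 56 (6.4), which are the three visits (5.5.1). The day-0 sample belongs to the randomisation visit (5.4) and cannot reflect imatinib.

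**Does anything earlier fill the gap?**
- The only blood draw between baseline and day 28 is the week-1 trough sirolimus level. It is taken only in participants on sirolimus, and no INR is planned with it (5.4, Table 2).
- The contacts at weeks 1 and 2 are telephone calls about side effects and adherence (5.5.3), with no laboratory test.
- The adverse-event definition in 6.3 includes a "clinically significant abnormal laboratory value or change in value", and under 6.3.1 the coordinator must "notify the site Principal Investigator and complete the Adverse Event Form within seven days of learning of the event". Section 6.4.1 allows removal of a participant who is unsafe. All of these need a result before they can operate.

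**Arithmetic**
- Time on drug with no repeat INR: 28 − 0 = 28 days, and 28/56 = 50% of treatment. At the planned dose that is 28 doses of 400 mg.
- Call windows: 7 ± 3 gives days 4 to 10; 14 ± 3 gives days 11 to 17.
- Gain from an INR at the first call: 28 − 10 = 18 to 28 − 4 = 24 days earlier than day 28.
- Gain from an INR at the second call: 28 − 17 = 11 to 28 − 11 = 17 days earlier than day 28.
- Enrolment cost of excluding warfarin, assuming 0 to 1 candidates lost: 0/20 = 0% to 1/20 = 5%.

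**A related inconsistency.** INR is in 5.5.1, 6.1.3 and 6.4 but is absent from the laboratory list in 4.4 and from Table 2. A site working from Table 2 could miss even the planned INRs.

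**The case against.** The strongest reply is that the investigators saw the interaction and responded to it by measuring INR in everyone at every visit. The dispute is then only about the interval. Since the documents give neither the size nor the speed of the interaction, they cannot show that 28 days is too long. That is fair as far as it goes, and for that reason the conclusion is confined to what the schedule can detect.

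Next, no exposed participant is shown. Warfarin use in this population is not described, and only half of the participants receive imatinib (10 sets of imatinib and 10 of placebo, section 6). This stands: it limits the expected harm and keeps the point minor.

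Third, warfarin may be handled elsewhere. Eligibility Screen Part 2 checks for contraindications (5.2), and the consent form and Manual of Operations may say more. None of these is in the documents, so the possibility stays open, but a known interaction belongs in the protocol's own criteria. The exclusion for other serious illness is worded around effects on the study outcome and does not name anticoagulation.

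Fourth, there are other safeguards: evaluation of worsening symptoms and reduction to 200 mg for persistent side effects (6.4). A participant's own clinic may also test her INR. The safeguards depend on something being noticed, and the protocol neither asks for outside INR tests nor has anyone alert the clinic.

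Finally, four other drugs are named beside warfarin. Warfarin is singled out here because INR is the test the plan itself chose for this interaction, and its timing can therefore be judged from the documents.

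**Conclusion.** The concern holds, as a minor point of participant safety. On the protocol text, a warfarin user may enrol, start imatinib 400 mg daily, and have no repeat study INR for 28 of 56 days. Telephone calls and adverse-event rules cannot detect a rise in INR that causes no symptoms.

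The conclusion rests on the protocol's own statement of the interaction and on its published schedule. It assumes that the screening form and other documents not supplied do not already exclude or monitor warfarin users. It makes no claim about the probability of bleeding, and the number of women affected may be zero. The statistical design and the VEGF-D comparison are not touched.

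**What to change.** Add required use of warfarin to the drug exclusion in 5.3.2. This is one line, with perhaps 0 to 1 candidates lost (an assumption; 0% to 5% of 20).

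If warfarin users must stay eligible, require for them alone an INR at about weeks 1 and 2, timed with the existing calls. Have the unblinded team in 5.6 review the results so that the blinded assessors do not see them. When the INR is above the participant's target range, adjust warfarin and repeat the INR, and name who makes the adjustment. This option costs more than it first appears. It needs two extra INR tests per warfarin user. The week-1 test can share the sirolimus draw in sirolimus users, but there is no week-2 draw and no interim draw at all for sirolimus-naive participants, so collection and reporting would have to be arranged. INR review would also be a new duty for a team now assigned only sirolimus levels. Exclusion is therefore the better choice.

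Under either option, add INR to the list in 4.4 and to Table 2 so that all parts of the protocol agree. This is an editorial change with no other cost.

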## 6.4.1 Withdrawal

A participant may withdraw from the study at any time for any reason. Study withdrawal for side effects is permitted. At the time of withdrawal the participant may 1) decline to provide any more data or specimens to the study but allow use of previously collected data and/or specimens, 2) request withdrawal of all his/her data from study databases and request that any stored samples be destroyed, or 3) withdraw some portion of the data collected (i.e., participants may withdraw specimens but not exam or questionnaire data or vice versa).

If a participant chooses to withdraw from the study, the research coordinator at the clinical site conducts an exit interview to determine the disposition of the participant's study data. The coordinator also provides the participant with any clinically relevant study results or establishes how the participant would like to be contacted if relevant results become available in the future. If the participant declines an exit interview, the consent form in place at the time of study withdrawal is used to determine the status of the participant's data.

Participants may be removed from the study if the clinical center PI determines that it is unsafe or unethical for the participant to continue in the study. Situations that might result in this kind of withdrawal include physical impairment such that the participant cannot complete the study protocol, institutionalization (e.g., long-term care facility, prison), or aggressive or antagonistic behavior towards clinical center staff. Any deterioration in symptoms or a 10% decline in either postbronchodilator FEV1 or FVC would end the study and participants can resume previous therapy.

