## 4.4 Laboratory Analysis

Samples of whole blood serum, DNA, blood mononuclear RNA, and urine will be obtained during this study. These samples serve the dual purpose of allowing a robust safety analysis of study timepoints and populating a LAM biobank of biosamples that are available to the larger LAM community (see Data Resource Sharing attachment). Biosamples will be stored both at Columbia University and MUSC and shared between laboratories with a sample and data sharing agreement in place with this study.

VEGF-D level will be measured at the beginning of the study, at one month and at the end of the study (56 days). For safety, all participants will also have laboratory monitoring of CBC, T4, TSH, Cholesterol, Sirolimus level and complete metabolic panel (CMP) at baseline, 28 days, and 56 days.

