## 7.3 Endpoints

**7.3.1 The primary efficacy analysis** will be the log transformed change in intrasubject plasma VEGF-D before and 1 month after initiation of monotherapy imatinib mesylate. Log transformation was needed in the MILES study because this serum concentration can often go quite high in some patients. VEGF-D will be obtained at baseline and at 28 and 56 days after initiation of imatinib. Note that this analysis will allow the use of sirolimus using and sirolimus naïve participants.

**7.3.2 Secondary endpoints** are obtained to test both efficacy and inform about quality of life. Quality of life questionnaire instruments are described in a later attachment as guided by the CDMRP program. Importantly, respiratory specific and general quality of life scores will be used in the study. Recently, the St Georges Respiratory Questionnaire (SGRQ) was retrospectively validated against four anchors in the MILES study and will be used as a secondary efficacy endpoint in the combined analysis of both stratified randomization populations. To minimize multiplicative analysis, 3 endpoints are chosen for combined population secondary endpoints: Intrasubject Change in FEV1 (ml), Intrasubject Change in FVC (ml), and Intrasubject Change in SGRQ (points) between the timepoints of Baseline and 1 month after initiation of monotherapy imatinib/placebo. The last secondary endpoint compares a 2 month treatment with imatinib/placebo in sirolimus naive participants on intrasubject change in log VEGF-D (pg/ml).

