## 7.4 Study Limitations

Study limitations include that the exact mechanism by which imatinib kills LAM cells remains unknown. The Bcr-Abl pathway has many downstream pathways including the Ras/MapK pathway, which leads to increased proliferation due to increased growth factor-independent cell growth. It also affects the Src/Pax/Fak/Rac pathway that affects the cytoskeleton leading to increased cell motility and decreased adhesion. The PI/PI3K/AKT/BCL-2 pathway is also affected altering mitochondrial stability. The JAK/STAT pathway, responsible for cellular proliferation is also affected by imatinib. While further laboratory studies on LAM/AML cells with alternative agents and mechanisms will continue, the current safety profile for imatinib use in humans is sufficient to begin a clinical trial in LAM prior to definitive mechanism of its effect on LAM cells is known.

The study is small and of short duration. The time interval for LAM cells *in vivo* to grow once removed from the influence of sirolimus is unknown. The study design in this rare disease is based on experience from LAM patients that remains anecdotal. However, in balancing safety and the potential to see a signal of efficacy in a pilot study, the current design is advanced.

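### Sections 6.4 and 6.4.1 disagree on worsening symptoms, and no VEGF-D draw is instructed at an early stop, so a baseline sirolimus user can leave after the 1-month visit without a primary value

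*Combined protocol and SAP*

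**What the plan says.** Section 6.4 on symptoms: "Any worsening of symptoms would prompt evaluation". In the same section a 10% fall in FEV1 or FVC "would prompt end of study, study unblinding, and transition to usual clinical care".

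Section 6.4.1, on the same two events: "Any deterioration in symptoms or a 10% decline in either postbronchodilator FEV1 or FVC would end the study and participants can resume previous therapy".

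Section 7.3 sets the sampling: "VEGF-D will be obtained at baseline and at 28 and 56 days after initiation of imatinib". Section 4.4 gives the same three times and places the end of the study at 56 days. At the 1-month visit (section 5.4), "Sirolimus will be discontinued if used at baseline"; this applies in both arms. The primary endpoint (sections 3.1 and 7.3) is the change in log VEGF-D to one month after monotherapy begins. Section 7.2 compares the arms with a two-sided rank-sum test at 0.05.

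The withdrawal procedure in section 6.4.1 is an exit interview about what happens to the participant's data. It contains no blood draw. Sections 7.2 and 7.3 define no analysis population, no rule for a missing Day 56 value, and no treatment of values taken after sirolimus is resumed.

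**The concern.** A participant who reports more breathlessness at the phone call two weeks after the 1-month visit is evaluated under one section. Under the other she is off study and free to restart sirolimus. Two sites could each follow the protocol and act differently.

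The statistical consequence falls on baseline sirolimus users, whom section 7.1 expects to be the majority. Their Day 28 sample is taken on sirolimus plus study drug, so Day 56 is their only scheduled value on study drug alone. If such a participant stops in between and no sample is taken, her primary value does not exist.

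The trigger for stopping is deterioration, and the protocol treats VEGF-D as a marker of disease activity (sections 2.1 and 4.2). The missing values may therefore be the high ones. If imatinib works, those would tend to be placebo participants with the largest rebound, and leaving them out would shrink the observed difference. Section 6.4 also unblinds on a 10% decline, so a handling rule left open could end up being chosen with some allocations known.

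**Working it through.** **1. The two rules side by side**

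| Event | Section 6.4 | Section 6.4.1 |
|---|---|---|
| Worsening symptoms | Evaluation | Participation ends; earlier therapy may resume |
| 10% fall in FEV1 or FVC | Participation ends, unblinding, usual care | Participation ends; earlier therapy may resume |

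The conflict concerns symptoms only. Both sections end participation on a 10% decline.

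**2. Who can lose the primary value**

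- Baseline sirolimus user stopping after the 1-month visit and before Day 56: scheduled values are baseline and Day 28, neither on study drug alone. Exposed.
- Sirolimus-naive participant stopping after Day 28: the Day 28 value is on study drug alone. Not exposed.
- Decline first found at the Day 56 visit: the sample is taken at that visit. Not exposed.
- Baseline sirolimus user stopping before the 1-month visit: never on monotherapy, so there is no such value to collect.

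Spirometry is scheduled only at visits. Between Day 28 and Day 56 the likely routes out are therefore symptoms, for example at the single scheduled call (section 5.5.3), or an unscheduled evaluation.

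**3. Size, under assumptions**

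There is no power figure in the plan to reproduce. Section 7.1 gives 20 participants without effect size, SD, power or dropout. The number only adds up: 10 + 10 by site (section 5.2) and 10 + 10 treatment sets (section 6). From the plan come 10 per arm and the two-sided 0.05 rank-sum test. The following are assumed:

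- SD of the natural-log change 0.4, mean rise 0.5 on placebo and 0 on imatinib.
- The k placebo participants with the greatest latent deterioration stop.
- Deterioration correlates 0.5 to 0.8 with the VEGF-D change.
- Only completers are analysed.

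The ratio can be checked by hand. The three largest of 10 standard normal values average (1.539 + 1.001 + 0.656)/3 = 1.065, so the remaining seven average −3 × 1.065/7 = −0.457. The placebo mean then falls by correlation × SD × 0.457:

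- correlation 0.5: 0.5 × 0.4 × 0.457 = 0.091, ratio exp(0.5 − 0.091) = 1.51
- correlation 0.8: 0.8 × 0.4 × 0.457 = 0.146, ratio exp(0.5 − 0.146) = 1.42
- full data: exp(0.5) = 1.65

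Power is from 20,000 simulated trials per scenario with the exact test:

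| Placebo stops | Power, completers | Ratio |
|---|---|---|
| 0 | 0.70–0.71 | 1.65 |
| 1 | 0.61–0.63 | 1.56–1.59 |
| 2 | 0.51–0.55 | 1.49–1.55 |
| 3 | 0.41–0.47 | 1.42–1.51 |

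**4. Separating bias from lost numbers**

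Three placebo values lost at random give power of about 0.60. So about 0.70 − 0.60 = 0.10 of the fall is sample size alone. The remaining 0.13 to 0.19 (0.60 − 0.47 to 0.60 − 0.41) comes from the stops being related to the outcome.

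**5. A second model, with stops in both arms**

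Here the true difference is 1.25 SD (0.5/0.4), 8 of 10 per arm are on sirolimus, and leaving is more likely with a larger rise. When 2.1 placebo and 0.5 imatinib participants are lost on average, power falls from 0.71 to 0.57 and the mean difference from 1.25 to 1.10 SD.

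**6. Type I error, no drug effect, three stops, completers only**

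- Imatinib stops unrelated to VEGF-D: about 0.043.
- The three worst deteriorators, in whichever arm: 0.044–0.046.
- Three stops all on imatinib and also correlated with VEGF-D: 0.06–0.11. With no drug effect and no other cause, all three fall on imatinib by chance in 120/1140 = 10.5% of trials.

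**The case against.** *The two sections can be read in sequence*: evaluate first, then stop if deterioration is confirmed. That is a sensible reading, and the fix adopts much of it. But section 6.4.1 does not say it, and neither section refers to the other.

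*An early draw may already be implied.* Section 5.4 heads the last visit "2 Month Visit/ End of study" and takes blood there, so an early end of study could be taken to trigger that visit. Section 4.4, however, ties the end of the study to 56 days, and the withdrawal text lists no draw. A draw is neither required nor forbidden. Section 10 mentions a Manual of Operations that is not among the documents, so the most that can be said is that the protocol itself gives no such instruction.

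*Frequency is unsupported.* This stands. A reader might infer frequent loss from section 2.1, where most women in the earlier sirolimus trial missed the next visit after stopping. That visit was three months away; the window here is one month.

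*The loss could favour imatinib.* A reader might infer this because both arms lose sirolimus and section 6.1.3 lists toxicities that could make imatinib participants stop. The documents do not link those toxicities to VEGF-D. The error rate stays near 0.045 unless stops are both confined to imatinib and correlated with VEGF-D. That reading is not supported.

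*No handling method is clearly better than completers-only.* This also stands. In simulations on the same assumptions, worst rank gave power of 0.76–0.82 with three placebo stops but 0.06 with two imatinib stops unrelated to VEGF-D. An early value helps only if much of the rebound is already present, and section 7.4 says the time for LAM cells "to grow once removed from the influence of sirolimus is unknown".

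**Conclusion.** The concern holds in a limited form. The symptom rules differ, and following the protocol as written can leave a baseline sirolimus user who stops between the 1-month visit and Day 56 without a primary value. Both points rest on the text alone.

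The size is conditional. If one to three placebo participants with larger rebound are lost and only completers are analysed, the result is biased toward no effect, with power and ratio as tabulated above. The SD, effect, correlation and number of stops are all assumed; the documents give neither the frequency nor the direction of loss. This is a cheap improvement to a small pilot, not a defect that invalidates its design.

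**What to change.** 1. **One symptom rule in sections 6.4 and 6.4.1.** Worsening symptoms trigger prompt evaluation with spirometry. A 10% decline in FEV1 or FVC, or the investigator's safety judgement, including on symptoms alone, ends participation. This is looser than section 6.4.1 as it stands, so symptoms alone must remain sufficient to stop.
2. **One sampling instruction.** It applies to any baseline sirolimus user who stops after the 1-month visit, and to any naive participant who stops early on study drug. With her agreement and without delaying care, carry out the planned final-visit VEGF-D draw, spirometry and SGRQ before sirolimus restarts and before unblinding. Record days off sirolimus.
3. **One analysis paragraph in section 7.2.** Exclude from the primary test any VEGF-D value taken after sirolimus resumes. Fix a single rule for early stoppers before unblinding, with completers-only as a sensitivity analysis. Report stops by arm and reason. The documents do not determine which rule is best, but one should be chosen in advance.

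The cost is an occasional unscheduled visit. It takes the place of the final visit if she stops; if she continues, it is a visit beyond the three for which section 5.2 provides travel money. She may decline the sample. An early value also reflects less than one month off sirolimus and may understate the rebound.
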